# **BRIEF DESCRIPTION OF THE PROJECT**

The burden of obesity has increased globally in recent decades and its association with insulin resistance and related cardio-metabolic problems. Radio frequency (RF) is a form of high-frequency electromagnetic energy that works by heating tissues. Its action aims to increase cellular metabolism. Its action aims to increase cellular metabolism. Frequencies around 1 MHz are used, which are more effective in the cell, but with high power, adjustable temperature and treatment area greater than 200 cm2, which mechanically destroys the adipose cells, without damaging the skin, blood, vessels, nerves or connective tissues.

The lymphatic system eliminates lidis, reducing tissue volume. Magnetic resonance imaging (MRI) has similar accuracy to CT scans, but with no exposure to ionizing radiation. The MRI method for quantifying abdominal adiposity is effective. Chronic inflammation that lasts a long time is characterized by the presence of lymphocytes, macrophages, proliferation of blood vessels and connective tissue, it is considered a feature of metabolic syndrome, characterized by secretion of inflammatory adipokines usually from adipose tissue, leptin, interleukin (IL-6), tumor necrosis factor  $\alpha$  (TNF- $\alpha$ ), monocyte chemoattractant protein 1 (MCP-1) and resistin. RNA markers involved in apoptotic processes revealed that tissue exposed to RF treatment demonstrated a pro-apoptotic reaction. Therefore, we propose to apply through four channels and four electrodes of 200 cm2 a powerful RF energy raising the temperature and thus reducing visceral fat, evaluating the biochemical parameters of inflammation of the adipocyte.

MAIN OBJECTIVE: To understand the effect of high-power resistive capacitive RF on the decrease of body fat and changes in biochemical markers linked to inflammation.

METHODOLOGY: at the inclusion visit, the patient will be given the information sheet (Annex 1) and, if they agree, they will be asked to sign the informed consent. We aim to declare a difference of 2 points or more as significant, taking the SD from published research that gives around 8.0 with a confidence level of 95%, a power of 80% and a correlation coefficient of 0.70 between the values of abdominal circumference before and after treatment. Noted by Duarte et al. in 2015. We have obtained by EPIDATA that 15 pairs are needed.

INCLUSION CRITERIA: Men and women aged 20 to 60 years. With Waist to Hip Index Greater than: 0.84 normal for women, 0.94 normal for men. Body Mass Index defined as: Overweight: Between 25-29.9 or Obesity: 30 or higher. Measurement of Visceral Fat (GV) by Inbody greater than 9 which is what is considered Normal. The GV value will be measured using the MRI method in addition to the MRI.

RADIOFREQUENCY PROCEDURE: Each patient will have 4 active, automatic plates placed on the abdomen located two on the right side of the midline and two on the left side. Energy will be applied for 50 minutes, controlling the temperature. Subsequently, 10 minutes of manual capacitive and resistive electrodes will be applied to the abdomen afterwards. 10 minutes of lymphatic drainage by placing one active plate in the foot and the other in the lumbo-dorsal area.

For the determination of biochemical parameters of inflammation and adipokines, the blood will be drawn in coordination with the Echevarne Accredited Clinical Laboratory in Barcelona. Its processing will be carried out at the Biomedical Research Institute of Malaga (IBIMA) Lipids and Arteriosclerosis Research Unit of University of Málaga. IL-6, TNF-alpha, leptin, human adiponectin, human resistin, human ultrasensitive C-reactive protein will be determined by ELISA and IMMUNOASSAY methods simultaneously. A Kolmogorov-Smirnov test will be applied,

if the data behaves normally, parametric tests will be applied. If not, non-parametric tests will be performed.

# PROJECT

# INTRODUCTION

The burden of obesity has increased globally in recent decades and its association with insulin resistance and related cardio-metabolic problems has negatively affected our ability to reduce population morbidity and mortality.

Traditionally, adipose tissue in the visceral fat deposition has been considered one of the main culprits in the development of insulin resistance. However, there is growing evidence supporting the role of subcutaneous trunk and abdominal adipose tissue in the development of insulin resistance, and more and more evidence supports the role of adipose tissue function in the development of metabolic complications independent of adipose tissue volume or distribution. Radiofrequency is an inexpensive, virtually side-effect-free, well-tolerated method that reduces belly fat.

## RADIOFREQUENCY AND FAT CELLS.

Radio frequency (RF) is a form of high-frequency electromagnetic energy that works by heating tissues. Its action in deeper tissues (subcutaneous layer) aims to increase cellular metabolism (van der Lugt et al 2009, Prumpa et al 2015). When applied to tissues, RF generates oscillating magnetic fields that move electrically charged particles, producing heat in the tissues, and the amount of heat produced depends on the resistance (bioimpedance) of the target tissue (Alexiades-Armenakas et al 2008, Kaplan and Gat 2009). Electrical energy is converted into thermal energy. There is evidence of a transient RF effect on autonomic homeostasis with no known negative effects. This autonomic response to RF is reflected in a thermoregulatory vasomotor mechanism, in changes in chemoreceptor activity, and even in fluctuations in the renin-angiotensin system, responses related to the control of energy metabolism. The elevation of tissue temperature appears to be sufficient to activate the sympathetic branch of the Autonomic Nervous System, leading to the release of catecholamines (adrenaline and noradrenaline), which are the trigger to activate lipolysis (Pumprla et al 2015, Belenky et al 2012, Ryden and Arner 2017). Lipolysis is the reversible biochemical process where triglyceride catabolism is stored. This process culminates in the generation of non-esterified fatty acids and glycerol. Fatty acids released into the bloodstream can be used as a substrate to produce energy (Pinto 2016).

The available literature on this topic still lacks information that would allow us to assume whether the effects of RF are reversible or not, and this process may depend on the temperature used and the exposure time. At the same time, tissue heating may also be related to vasodilation and increased perfusion and local oxygenation that promote oxidation and lipid turnover that will culminate in a decrease in adipose cell volume (Mulholland et al 2011). Considering that the processes enhance each other, improving blood perfusion and hormone flow could make lipolysis more efficient.

Ex vivo human skin cultures after completion of the RF treatment series showed a profound effect on subcutaneous adipocytes. Adipocyte cells were observed to have altered morphology and increased expression of the apoptosis marker, APAF-1, suggesting that RIE-induced apoptosis is the mechanism of action. Adipocyte apoptosis results in the release of triglycerides

from disintegrated cell membranes, but in a delayed and gradual manner, allowing for slow and safe elimination through the interstitial space, and subsequent lipid transport systems, lymphatic systems, and other metabolic functions. There was no evidence of necrosis or inflammatory changes observed in adipocytes after treatments with this new RF device. While IRE has been shown to be effective in inducing cellular apoptosis in other tissues, to our knowledge, this is the first documentation of IRE in adipose tissue with RF treatments.

It is known that adipose tissue, apart from serving as an energy storage site, has an endocrine function by secreting multiple proteins known as adipokines.

Obesity causes an increase in adipose tissue and an increased infiltration of inflammatory cells into that tissue. The expansion of TA is associated with an altered pattern of fat tissue cytokines with a predominance of pro-inflammatory cytokines (TNF- $\alpha$ , IL-6 among others) and a decrease in anti-inflammatory cytokines, resulting in the development of a chronic low-intensity inflammatory state.

The chronic low-intensity inflammatory state causes a state of insulin resistance at the level of muscle and liver tissue due to lipid accumulation in these tissues and organs, resulting in the pathological condition known as non-alcoholic fatty liver.

#### RADIOFREQUENCY AND LIPOLYSIS

Adipocytolysis is a term used to describe the phenomena caused by non-surgical techniques (cytolytic methods) for the reduction of localized fat, in which lipids could be broken or solubilized through the partial or total rupture of adipocytes, destroying their plasma membrane (Pereira et al. 2017).

Treatments combining non-thermal forms of focused ultrasound and radiofrequency treatment have been performed for body contouring in the abdominal region and it has been concluded that it is effective and can show positive results for at least one year if patients maintain body weight (Chang et al. 2016).

Frequencies around 1 MHz are used, which are the ones that act most effectively on the cell, but with a high power, adjustable temperature and a treatment area greater than 200 cm2, which allows it to mechanically destroy the adipose cells, with greater effectiveness in the subcutaneous adipose tissue without damaging the skin. blood, vessels, nerves, or connective tissues. Lipids are gradually eliminated through the lymphatic system, reducing tissue volume. Previous studies have shown that single or multiple treatments with these devices are effective, safe, and comfortable for the abdomen, flanks, and thighs. The average girth reduction of three treatment regimens ranges from 2.9 to 3.95 cm (Fritz et al. 2018, Hart 2015).

This procedure has been used quite effectively in aesthetics to reduce subcutaneous fat. A recent study highlights the efficacy of this RF treatment modality in primarily tightening the skin and reducing fat. (Mazzoni et al) Another recent study has pointed to the use of 1 MHz monopolar RF in body contouring, for fat reduction and tightening of the lower face. On the other hand, he has pointed out that this treatment can maintain a fixed therapeutic temperature and is very effective in reducing fat and tightening the lower part of the face (Sugawara et al. 2017).

#### **BIOCHEMICAL MARKERS**

Inflammation is an orderly sequence of events designed to maintain homeostasis of organs and tissues. Timely release of mediators and expression of receptors are essential to complete the sequence of events and restore tissues to their original condition [1]. In addition, inflammation is a protective tissue response to injury or tissue destruction that serves to destroy or dilute both the damaging agent and the injured tissues. There are two types of inflammation; The first is an acute inflammation that lasts a short time and is characterized by edema and leukocyte migration, and the second is a chronic inflammation that lasts a long time and is characterized by the presence of lymphocytes and macrophages and the proliferation of blood vessels and connective tissue. This is considered a characteristic feature of metabolic syndrome, characterized by the secretion of inflammatory adipokines usually from adipose tissue, such as leptin, interleukin (IL-6), tumor necrosis factor  $\alpha$  (TNF- $\alpha$ ), monocyte chemoattractant protein. 1 (MCP-1) and resistin. Obesity, which is a feature of metabolic syndrome, was associated with chronic inflammation in obese subjects. Several inflammatory indicators are linked to obesity and shed light on the associated health complications. Inflammatory indicators include IL-6 and C-reactive protein (CRP) as inflammatory markers and adiponectin as an anti-inflammatory marker (Ellulu et al 2017). In summary, when adipose tissue increases more than expected, a cytokine imbalance appears that increases the release of pro-inflammatory cytokines such as TNF- $\alpha$ , IL-6, IL-1 $\beta$ , resistin, and leptin, while adiponectin, which is anti-inflammatory, decreases. This imbalance results in chronic, low-grade inflammation. Hence the importance of measuring these parameters to assess the anti-inflammatory effect of the treatment.

Sustained inflammation is considered a major risk factor for developing many diseases, including cardiovascular disease, metabolic syndrome, diabetes, and cancer. As a risk factor, obesity predisposes to a pro-inflammatory state through the increase of inflammatory mediators IL-6 and TNF- $\alpha$ , and reduced levels of adiponectin, which has a totally anti-inflammatory function. According to Badawi et al. 2010, TNF- $\alpha$  is overexpressed in overweight status, while IL-6 is more related to obesity status influencing the liver to synthesize and secrete CRP, which is a feature of systemic inflammation. This state is associated with reduced levels of adiponectin, which is important for improving insulin sensitivity, reducing metabolic abnormalities, and adjusting energy expenditure. In addition, the inflammatory state followed by vascular and endothelial dysfunction is characterized by a decrease in nitric oxide and an increase in reactive oxygen species leading to oxidative stress. Both states of oxidative stress and inflammation initiate atherosclerosis, hypertension, alteration of metabolic markers, and thus major adverse cardiovascular events. Hence the importance of studying these markers before and after treatment.

RF treatment induces an increase in the apoptotic index in adipocytes 1 hour after RF treatment. This is accompanied by a maximum temperature of 45°C in the grease layer. Skin surface temperatures remain substantially lower than fat temperatures. (McDaniel & Lozanova 2015). The application of RF has shown greater increases in TNF- $\alpha$  Pro-Apoptotic Markers. Analysis of RNA markers involved in apoptotic processes revealed that tissue exposed to RF treatment demonstrated a pro-apoptotic reaction. Several studies have documented the role of TNF- $\alpha$  in adipocyte apoptosis (Weiss & Bernardy 2019).

#### VISCERAL FAT MEASUREMENT BY IMAGE

While computed tomography (CT) is the most commonly used imaging modality for measuring abdominal fat, magnetic resonance imaging (MRI) has similar accuracy (Klopfenstein et al 2012). An advantage of MRI is the absence of exposure to ionizing radiation, a limitation that restricts the use of CT in children and adolescents. In addition, the MRI method for quantifying abdominal

adiposity is effective, allowing imaging within 5 minutes. Magnetic resonance imaging can provide reliable and good quality images for visceral and subcutaneous quantification (Eloi et al 2017).

With the scanning parameters employed, fat appears as a loud signal against a muted background of other tissues and noise. The images were segmented and analyzed using a software program that employed knowledge-based image processing to label voxels as fatty and non-fat components. The image processing and/or analysis procedure employed a contour tracking algorithm to isolate individual structures from binary images produced by thresholding. The threshold required to identify voxels associated with grease components was automatically calculated from gray intensity histogram analysis and background noise calculation.

The adipose tissue volumes (cm3) of each compartment were calculated by adding the relevant voxel counts and multiplying by the voxel dimensions in cubic centimeters. The volume of adipose tissue for the entire abdomen was calculated by multiplying the volumes of adipose tissue from each slice by the sum of the thickness of the slice (5 mm) and the distance between slices. This analysis provides a direct measurement of adipose tissue volume. Adipose tissue in grams is calculated from the following formula:

Fat mass (g) = Adipose tissue volume cm3 x 0.66 g/cm3

For all of the above, we propose to apply through four RF channels and four 200 cm2 electrodes a powerful energy raising the temperature and thus reducing visceral fat by evaluating the biochemical parameters of adipocyte inflammation.

## OBJECTIVES

MAIN OBJECTIVE.

- To understand the effect of high-power resistive capacitive radiofrequency on the decrease of body fat and changes in biochemical markers linked to inflammation.
  SIDE OBJECTIVES.
  - 2. To assess the role of radiofrequency in reducing abdominal fat.
  - 3. To assess and compare the decrease in abdominal circumference measured by anthropometric tape measure, Body Mass Index, Waist-to-Hip Ratio and skinfold before and after RF treatment.
  - Evaluate changes in Human IL-6, Human TNF-alpha, Human-Leptin, Human-Adiponectin, Human-Resistin, C-reactive protein values before and after RF sessions. Evaluar y comparar el impacto de la calidad de vida antes y después del tratamiento con radiofrecuencia.
  - 5. To assess and compare the impact of quality of life before and after radiofrequency treatment.

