#### METHODOLOGY

At the inclusion visit, the patient will be given the information sheet (Annex 1) and, if they agree, they will be asked to sign the informed consent. Once included in the study, they will be randomly assigned to one of the two study groups in order of consecutive inclusion.

The project will be presented to the Ethics Committee of the Autonomous University of Barcelona UAB.

SAMPLE SIZE CALCULATION

The aim of this study was to assess the difference between a decrease in the diameter of the abdominal circumference in a group of women, before and after radiofrequency treatment. The aim is to be able to declare a difference of 2 points or more as significant, taking the SD from published research that gives around 8.0 with a confidence level of 95%, a power of 80% and a correlation coefficient of 0.70 between the values of abdominal circumference before and after treatment. These are taken from the article published by Duarte et al. in 2015 (Duarte et al, 2015), and the following results are obtained according to EPIDATA: 15 pairs of data will then be taken: Before and after the application of RF.

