# **Objective of the study:**

- 🛠 Main
  - Decrease in body fat and biochemical markers.
- Secondary
  - Reduction in abdominal fat.
  - Decrease in abdominal circumference, body mass index.
  - Changes in glycemia, cholesterol and triglycerides.
  - Evaluate and compare the impact of quality of life.

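### The documents disagree on the main outcome: the only power calculation is for abdominal circumference, ranked as a side objective, so the stated 80% does not cover the main objective of body fat plus markers

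*Combined protocol and SAP*

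**What the plan says.** **Rank of the outcomes.** The Objectives section, like the brief description at the front, gives the main objective as the effect of radiofrequency on "decrease of body fat and changes in biochemical markers linked to inflammation". The later Study Protocol part agrees: under its objective heading the main item is "Decrease in body fat and biochemical markers". Circumference ranks lower in both lists. In Objectives it is side objective 3 ("To assess and compare the decrease in abdominal circumference measured by anthropometric tape measure"), and in the Study Protocol part it is secondary ("Decrease in abdominal circumference, body mass index").

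**Sample size.** The Methodology section takes another view: "The aim of this study was to assess the difference between a decrease in the diameter of the abdominal circumference in a group of women". The calculation there uses a 2-point difference, an SD of about 8.0, 95% confidence, 80% power and a "correlation coefficient of 0.70 between the values of abdominal circumference before and after treatment". The output table beneath it shows a difference of 6.442, an SD of differences of 8.221 and 15 pairs. The brief description repeats the 2-point inputs and the 15 pairs. No other outcome has a size calculation.

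**Markers and body fat.** The six markers are named among the side objectives: "Evaluate changes in Human IL-6, Human TNF-alpha, Human-Leptin, Human-Adiponectin, Human-Resistin, C-reactive protein values before and after RF sessions". Visceral fat is measured by both MRI and Inbody impedance.

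**Analysis.** The statistical analysis section lists a normality check, t-tests with non-parametric alternatives, an exact test for proportions and Pearson correlation. It gives no primary outcome, significance level or multiplicity rule.

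**The two lists differ.** "Changes in glycemia, cholesterol and triglycerides" appears only in the Study Protocol list. Waist-to-hip ratio and skinfold appear only in the Objectives list.

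**The concern.** A power statement belongs to one outcome, one effect size and one SD. Here it belongs to an outcome that both objective lists put below the main objective, while the main objective has no effect size, no SD and no designated measure. Two things are at stake. A reader may attach 80% power to body fat or to a marker, for which none was computed. And because the main objective covers several outcomes with no rule for combining or ordering them, nobody can say beforehand which results would count as a positive trial, or what the chance of a false positive is.

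**Working it through.** **1. The plan's own figure.** Inputs from the output table: difference 6.442, SD of differences 8.221, 95% confidence, 80% power. Sidedness is not stated.

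- Standardised difference: 6.442 / 8.221 = 0.784.
- Two-sided normal approximation: ((1.960 + 0.842) × 8.221 / 6.442)² = 12.8, so 13 pairs.
- Exact two-sided paired t-test: 15 pairs, power 80.6%. A one-sided test would need 12.

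The stated 15 pairs is reproduced by the two-sided paired t-test with the table's inputs.

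**2. The same calculation with the inputs in the text.** The Methodology and the brief description give 2 points, SD 8.0 and r = 0.70. I read 8.0 as the SD of a single measurement, equal before and after.

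- SD of differences: 8.0 × √(2 × (1 − 0.70)) = 8.0 × √0.6 = 6.20.
- Power at 15 pairs, two-sided 5%: 21%.
- Pairs needed for 80%: 78.
- If 8.0 is instead taken as the SD of differences: 15% power at 15 pairs, and 128 pairs needed.

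So even for circumference the 80% depends on the table's inputs.

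**3. Power for the main objective.** It cannot be computed, because the documents give no effect or SD for body fat or any marker. With 15 pairs at two-sided 5%, 80% power needs a standardised paired difference of about 0.78, whatever the outcome. Nothing in the documents says whether body fat or any marker would reach that.

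**4. Illustration of the false-positive chance.** Assumptions: seven tests (one body-fat measure plus six markers), each two-sided at 5%, with no true effects.

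| Dependence between tests | Chance of at least one false positive |
|---|---|
| Independent: 1 − 0.95⁷ | 30.2% |
| Pairwise correlation 0.3 (simulated) | about 27% |
| Pairwise correlation 0.5 (simulated) | about 24% |
| Upper bound: 7 × 0.05 | 35% |

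The simulated rows are paired t-tests at n = 15, 20,000 runs. Under independence the count matters modestly: six markers alone give 1 − 0.95⁶ = 26.5%, and eight tests (MRI and Inbody both counted) give 1 − 0.95⁸ = 33.7%.

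**5. Cost of Holm across six markers.** No marker effect is available, so I borrow the circumference value of 0.784 as an assumption. Power at 15 pairs is 80.6% at 5% and 50.9% at the strictest step, 0.05/6 = 0.0083.

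**The case against.** The strongest reply is that the Methodology section does name circumference as the study's aim. On that reading the main objective is a broad statement of purpose made concrete by the side objectives, and the power calculation is attached to the right outcome. This stands in part: one cannot simply say that the trial was powered for the wrong outcome. But the Methodology sentence contradicts the rank given in both objective lists, and nothing in the documents settles which prevails.

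Some stronger readings are tempting, and the documents do not support them:

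- *Each marker is tested at 5%.* No level is stated for any test. The 95% confidence appears only in the sample size calculation. Taking 5% is a default reading, since no adjustment is planned.
- *Any one of seven results would count as success.* There is no success rule at all. The supportable statement is that success is undefined.
- *The plan's error rate is 30%.* The count of seven is an assumption: the main objective mentions the markers only collectively, body fat is measured in two ways, and independent-samples tests are also listed.
- *Glucose and lipids will not be measured.* The assay section covers only inflammation markers and adipokines, and the Study Protocol part mentions costed tests without itemising them. Only the mismatch between the two lists can be shown.

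It might also be said that a small study needs no such structure. The documents, however, do not call the study exploratory, and they set out to declare a difference significant with stated power.

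**Conclusion.** The concern holds as an internal contradiction about the main outcome with two consequences. First, the 80% power was derived for circumference alone and does not extend to body fat or any marker; for those outcomes no power is stated and none can be computed. Second, with no primary outcome, significance level or multiplicity rule in the statistical section, the trial does not define what a positive answer to its main objective is.

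The 24% to 30% chance of a false positive shows what is at risk under seven tests at 5% and correlations from 0.5 down to 0. It is not a property that the plan states. The points about rank, missing power and missing rules rest on the text alone and need none of those assumptions. The conflict between 2 points and 6.442 is a further defect, and it bears on the remedy: promoting circumference to primary does not by itself secure 80% power.

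**What to change.** 1. Name abdominal circumference as the single primary outcome in the Objectives, the Methodology and the Study Protocol's objective list, and align the main objective in the brief description.
2. State that the 80% power refers to circumference alone, and only for a mean difference of 6.442 with SD of differences 8.221. Reconcile this with the 2 points, SD 8.0 and r = 0.70 in the Methodology and brief description, and restate the power.
3. Make body fat and all other outcomes secondary. If significance is to be claimed for the six inflammation markers, apply Holm across them. State the significance level and sidedness in the statistical section.
4. Use one objective list throughout, with glycemia, cholesterol, triglycerides, waist-to-hip ratio and skinfold either in it or out of it.

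Cost: items 1, 3 and 4 are mainly wording, though keeping glucose and lipids would mean confirming that they are assayed. Item 2 may cost more: if the 2-point difference is the intended target, the inputs in the text call for 78 pairs, not 15. Holm lowers power per marker, from 81% to 51% at its strictest step under the borrowed effect size. If the investigators prefer a body-fat measure as primary, they will need an effect size and SD that the documents do not contain.
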